We propose to perform a multi-center study in which adult kidney transplant recipients with proteinuria (≥ 1 g/day) will be converted from CNI to Belatacept (**Figure 3**) once B7-1 staining has been performed on allograft biopsy ([name] will be performing all stains). This is a Phase I study that will aim to enroll 36 patients in 18-month recruitment time involving 3 transplant sites. Other inclusion criteria include: eGFR > 30 ml/min, greater than 6 months post-transplant and EBV IgG positive status. **Exclusion criteria** include: age < 18 years, eGFR < 30 ml/min, active acute cellular rejection (ACR; higher than borderline) or ACR in the previous 6 months, recurrent FSGS, EBV IgG negative status and on mTOR inhibitor as maintenance immunosuppression.

[figure not shown]

Figure 3. Study Design. Protocol and outcomes measures are detailed.

Patients that develop proteinuria after transplant are a heterogenous group with many potential

underlying etiologies including calcineurin inhibitor toxicity, transplant glomerulopathy, BK nephropathy or recurrent glomerular disease (4). Therefore, we decided to enroll 12 patients per center (3 centers total) to allow the inclusion of different etiologies of proteinuria and be a feasible study based on our inclusion criteria.

By including both B7-1 positive and B7-1 negative patients with proteinuria in the study, we will have the best chance of success and it would also allow for future testing for other potential prognostic markers in this population. One of the main reasoning's behind this is that the B7-1 staining is undergoing further optimization by [name] and a NIH task force, and therefore, restricting our recruitment may limit interpretation of the data in case the staining changes. This has been previously shown to be most productive approach in biomarker-driven interventions in the cancer field (11). In addition, the exact mechanism in which B7-1 targeting reduce proteinuria is still debated. By including both B7-1 positive and B7-1 negative patients with proteinuria, we will be able to assess overall risk factors and have a control group with no B7-1 staining treated with Belatacept. A historical control group with patients that fit the inclusion criteria and were managed as standard of care at our institution will also be included for comparison.

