All study investigators and study staff must follow all appropriate requirements, including Good Clinical Practice (GCP), International Conference on Harmonization (ICH), Code of Federal Regulations (CFR), and the Partners Human Research Committee (PHRC) Institutional Review Board (IRB). The study will be conducted in compliance of the protocol. The protocol, all amendments, and the subject informed consent will receive Institutional Review Board/Independent Ethics Committee (IRB/IEC) approval/favorable opinion before initiation of the study. Study personnel must be qualified by education, training and experience to perform their respective tasks, and will not utilize personnel for whom sanctions have been invoked or where there has been scientific misconduct or fraud.

Appropriate study personnel will obtain signed and dated informed consent from each study participant. [Investigators will ensure that subjects, or their legally acceptable representatives, are clearly and fully informed about the purpose, potential risks, and other critical issues regarding this clinical research study in which they voluntarily participate. The approved consent form will adhere to the ethical principles that have their origin in the Declaration of Helsinki. All relevant safety information regarding the dose/schedule of study drug, or any other drugs/procedures in this clinical study must be explained in the informed consent document. Informed consent will also delineate which authorities may have direct access to study records and documents. Consent will also clearly state that although [name] is the study sponsor, Bristol-Myers Squibb (BMS) is the study funding source and is also supplying study drug for this study.

7. Eligibility:

7.1 Inclusion Criteria:

- Deceased or living donor adult kidney transplant recipients older than 18 years old
- eGFR >30 ml/min
- >6 months after transplantation
- Proteinuria >1 gram/day in spot urine protein/creatinine ratio
- Available biopsy specimen for B7-1 staining at recruitment time.
- Ability to provide written informed consent for the study.
- Must be EBV IgG positive

7.2 Exclusion Criteria:

- Age <18 years
- eGFR<30 ml/min
- Active acute cellular rejection (ACR; higher than borderline) or ACR in the previous 6 months; active acute antibody-mediated rejection.
- Recurrent FSGS
- EBV IgG negative

- Patient on mTOR inhibitor (e.g. Everolimus, Sirolimus)
- Age and Reproductive Status:

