The primary endpoint of the study will be a 25% reduction in proteinuria from baseline to 12 months. This endpoint was extrapolated from studies with ACE inhibitors showing significant benefit in patients with kidney disease and proteinuria that reached this endpoint (12). For comparison, we will also have a historical control group with patients that fit the inclusion criteria and were managed as standard of practice on our institution. A logistic regression model will be used to control for key variables such as baseline ACEI/ARB use, level of proteinuria, age and gender.

For the primary endpoint: Percentage of those patients who have a $\geq 25\%$ reduction in proteinuria from baseline to 12 months will be reported separately for each group. We will compare these percentages between the two groups using Fisher's exact test. In addition, means and standard deviations of the actual reduction will be reported separately for each group and will be compared between the two groups using a non-parametric test (Wilcoxon rank-sum). These results will also be compared to historical controls. A logistic regression model will be used to control for key variables such as baseline ACEI/ARB use, level of proteinuria, age and gender.

For the secondary endpoints: Descriptive statistics (means, standard deviations and/or percentages) will be reported on percent change of renal function from baseline to 12 months; donor-specific anti-HLA antibodies presence and intensity (MFI); adverse events; acute rejection episodes; blood pressure control; new onset diabetes; and hyperlipidemia. Spearman correlations will be calculated between B7-1 positivity on immunofluorescence on biopsy with B7-1-expression in urine extracellular vesicles. Kaplan-Meyer plots will be used to study graft survival and patient survival and a proportional hazards model will be used here to compare survival between treated and historical controls, controlling for the baseline covariates above.

References:

2. Halimi J-M. Low-grade proteinuria and microalbuminuria in renal transplantation. *Transplantation*. 2013;96(2):121-30.

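### The historical controls are defined by the inclusion criteria alone; as written, they may have active or recent rejection or recurrent FSGS, which bar treated patients

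*Combined protocol and SAP*

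**What the plan says.** The historical controls are defined in two places. Section 6 (Proposal) has "A historical control group with patients that fit the inclusion criteria and were managed as standard of care at our institution". Section 11 (Statistics) has a "historical control group with patients that fit the inclusion criteria and were managed as standard of practice on our institution". Neither sentence mentions the exclusion criteria.

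For treated patients the protocol keeps two separate lists. Section 6 itself gives them one after the other: "Other inclusion criteria include: eGFR > 30 ml/min, greater than 6 months post-transplant and EBV IgG positive status", then exclusions that include "active acute cellular rejection (ACR; higher than borderline) or ACR in the previous 6 months, recurrent FSGS". Section 7.2 excludes "Active acute cellular rejection (ACR; higher than borderline) or ACR in the previous 6 months; active acute antibody-mediated rejection" and, as a separate item, "Recurrent FSGS". The synopsis also lists these conditions under exclusions only.

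Section 11 uses the controls in two ways. The primary-endpoint results are to be compared with them, in addition to the tests between the two groups, which are apparently B7-1 positive and negative. They are also the named comparator in the proportional hazards model for graft and patient survival. The covariates named for adjustment are baseline ACEI/ARB use, level of proteinuria, age and gender; the list is worded as examples.

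**The concern.** Every enrolled patient is converted to Belatacept, so the contrast by B7-1 status cannot show what would have happened without conversion. Only the historical comparison addresses that, and even there the contrast combines starting Belatacept with stopping the CNI.

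If the control rule is followed literally, one side of that comparison can contain patients with rejection or recurrent FSGS and the other side cannot. These conditions can affect both proteinuria and graft survival. The protocol itself treats them as relevant: Section 8.1.1 discusses rejection as a predictor of long-term outcome, and Section 2 names recurrent glomerular disease as the second most common cause among heavily proteinuric patients with glomerular pathology. A one-sided difference in case mix could then be read as an effect of conversion, or could hide one.

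**Working it through.** No figure in the plan needs to be reproduced. The check is to take each exclusion and ask whether an inclusion criterion already covers it. Only those without a counterpart are lost when controls are selected on inclusion criteria alone.

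| Condition | Where it excludes treated patients | Inclusion counterpart |
|---|---|---|
| Active acute cellular rejection above borderline | Synopsis, Section 6, Section 7.2 | None |
| Acute cellular rejection in the last 6 months | Synopsis, Section 6, Section 7.2 | None |
| Active acute antibody-mediated rejection | Synopsis, Section 7.2 (not in Section 6) | None |
| Recurrent FSGS | Synopsis, Section 6, Section 7.2 | None |
| mTOR inhibitor use | Synopsis, Section 6, Section 7.2 | None in Section 7.1; largely covered by synopsis inclusion item 7 |
| Only CNI and steroids | Synopsis only | Covered by synopsis inclusion item 7 |
| Age, eGFR, EBV status | All three places | Yes |

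The gap therefore falls on the four conditions in the first four rows. For antibody-mediated rejection only active disease is barred; the 6-month look-back applies to cellular rejection.

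**Can the planned adjustment close the gap?** None of the four conditions is a named covariate. The list is open, so one could be added. But by rule no treated patient has the condition, so such a term would be estimated among controls only and would in effect set those controls aside. It would also leave the unadjusted percentages and the Kaplan-Meier plots untouched.

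**Can the exclusions be applied as they stand?** Not without a date. The time since transplantation, the biopsy available at recruitment and the 6-month look-back all refer to a point in time, and a historical patient has no recruitment date. The change from baseline to 12 months and the survival clock need the same anchor. The document gives none for controls.

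**Is there one list to apply?** Not quite. Synopsis inclusion item 7 (CNI plus an antiproliferative agent) is absent from Section 7.1. The synopsis thresholds for eGFR, time since transplantation and proteinuria include the boundary value, while those in Section 7.1 do not.

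**Size.** If a share of controls had an excluded condition, the control response rate would move by that share times the difference in response between those controls and the eligible ones. The documents give neither quantity, nor the number of controls. The sign is open as well. Controls with progressive rejection or recurrent disease could do worse, which would favour Belatacept. Controls whose proteinuria falls once a rejection episode is treated could do better, which would count against it.

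**The case against.** The strongest reply is that this is loose wording. Section 6 says the study will "be a feasible study based on our inclusion criteria", and feasibility depends on full eligibility, so the authors may use the phrase as shorthand for both lists. That reading is possible. But no sentence confirms it, and Section 6 elsewhere lists exclusions separately from inclusions. The converse is not supported either: a reader might infer that the sponsor meant to admit controls with rejection or FSGS, and nothing in the text shows such an intention.

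The second reply is that the comparison is minor. This is a Phase I study of 36 patients, sized on feasibility with no power claim, and the historical comparison of proteinuria is additional to the Fisher and Wilcoxon tests. Survival results will probably be imprecise however controls are chosen. This limits the weight of the point and stands to that extent. It does not remove the point, because these controls are the only non-Belatacept comparator and the stated one in the survival model.

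**Conclusion.** The point holds as a defect in the written selection rule. Followed exactly, the rule allows into the control group four conditions that bar every treated patient, and neither the inclusion criteria nor the named covariates deal with them. It affects the supplementary proteinuria comparison and the graft and patient survival model. The planned tests between the two groups are not affected, on the reading that those groups are B7-1 positive and negative. Whether any such control would actually be selected depends on how the sponsor applies the phrase.

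Three stronger conclusions are tempting but unsupported.

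- A reader might infer that the rule flatters Belatacept. The direction cannot be known from the documents.
- A reader might try to size the bias from Section 2, which reports glomerular pathology in more than 80% of patients above 1500 mg/d and recurrent glomerular disease in 25% of those. Those figures do not separate FSGS, describe a population above the 1 g/day entry level, and say nothing about rejection or about how response differs.
- A reader might infer from the 60 days shown at Day 1 in the Schedule of Events that treated patients have a guaranteed event-free period that controls lack. That table header is broken in the available text, and the plan states no time origin for controls and no horizon for the survival analysis, so this cannot be established.

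**What to change.** In Sections 6 and 11, state that historical controls must meet every inclusion criterion that can be verified from records, and no exclusion criterion, at a defined index date. State that this date is also their baseline for the 12-month proteinuria change and their time origin for graft and patient survival. Apply the same eligibility list to treated patients and controls, which requires the synopsis and Section 7 to be reconciled first. Name the criteria that cannot be checked retrospectively, such as consent. Settle all this before controls are selected, so that the choices do not depend on known outcomes.

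If full eligibility was always meant, the protocol change is one of wording. Otherwise the cost is some extra chart abstraction (rejection history, FSGS status and the index date) and a somewhat smaller control pool.

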Secondary: Assess the effect of Belatacept conversion in the percent change of renal function from baseline to 12 months; donor-specific anti-HLA antibodies presence and intensity (MFI); correlation of B7-1 positivity on immunofluorescence on biopsy with B7-1-expression in urine extracellular vesicles; adverse events; acute rejection episodes; blood pressure control; new onset diabetes; hyperlipidemia; graft survival; and patient survival.

Study design:

Inclusion Criteria:

1. Male or female adult kidney transplant recipients older than 18 years old
2. eGFR $\geq 30\text{ ml/min}$
3. ≥ 6 months after transplantation
4. Proteinuria $\geq 1\text{ gram/day}$ in spot urine protein/creatinine ratio
5. Available biopsy specimen for B7-1 staining at recruitment time.
6. Ability to provide written informed consent for the study.
7. Maintenance immunosuppression of CNI (cyclosporine or tacrolimus), antiproliferative agent (azathioprine, MMF or MPA) with either steroids or not.
8. Must be EBV IgG positive

Exclusion Criteria:

1. Age < 18 years

2. eGFR<30 ml/min
3. active acute cellular rejection (ACR; higher than borderline) or ACR in the previous 6 months; active acute antibody-mediated rejection.
4. recurrent FSGS
5. EBV IgG negative
6. patient on mTOR inhibitor (e.g. Everolimus, Sirolimus)
7. patient only on CNI (cyclosporine or tacrolimus) and steroids

Accrual Goal: 36 subjects, 3 study sites

Accrual Rate: approximately 2 subjects/month; total of 18 months enrollment; 18 months of follow-up

First Patient First Visit: 1-March-2015

Statistics: This is a Phase I clinical trial to test the safety and gain further insight into the potential effect of Belatacept in proteinuric kidney transplant patients. We plan to recruit 36 patients, based on the feasibility for recruitment in 3 transplant centers and prior literature on recommended sample sizes in a Phase I trial.

2. Background:

Although improvements in immunosuppression have led to a reduction in acute rejection rates, long-term allograft survival remains disappointing, with more than 50% of allografts lost 10 years after transplantation.

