Using a goat anti-human B7-1 (CD80) antibody, we performed immunostaining for B7-1 on frozen sections of **123 clinically indicated kidney transplant biopsies** obtained between 2011 and 2012. Fifteen patients had $\geq 1+$ B7-1 staining on glomeruli at podocyte location (**Figure 2**). The predominant pathologic diagnosis among those with B7-1 positivity was **transplant glomerulopathy** (46%). In addition, 27% of patients with $\geq 1+$ B7-1 staining in their biopsies had nephrotic range proteinuria (4 out of 15) and 50% of allograft biopsies obtained from patients with nephrotic syndrome stained positive for B7-1 (4 out of 8). In sum, **B7-1 is expressed at significant levels in about 10% of kidney allograft biopsies.**

[figure not shown]

Figure 2. B7-1 staining in kidney transplant biopsies.

4. Hypothesis:

We hypothesize that B7-1 targeting therapy may reduce proteinuria and improve graft survival in proteinuric transplant recipients that have B7-1 staining on allografts. In addition, the absence of CNI nephrotoxicity and the potential protective effect of Belatacept on DSA production may be of benefit in this subset of transplant patients (9, 10).

5. Objectives:

Primary: Determine the effect of Belatacept conversion in reducing proteinuria by 25% at 12 months in renal transplant recipients that have more than 1 gram of proteinuria per day and are either B7-1-positive or negative on kidney biopsy.

Secondary: Assess the effect of Belatacept conversion in the percent change of renal function from baseline to 12 months; donor-specific anti-HLA antibodies presence and intensity (MFI); correlation of B7-1 positivity on immunofluorescence on biopsy with B7-1-expression in urine extracellular vesicles; adverse events; acute rejection episodes; blood pressure control; new onset diabetes; hyperlipidemia; graft survival; and patient survival.

6. Proposal:

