The **primary endpoint** of the study will be a 25% reduction in proteinuria from baseline to 12 months. This endpoint was extrapolated from studies with ACE inhibitors showing significant benefit in patients with kidney disease and proteinuria that reached this endpoint (12). **Secondary end-points** include: percent change of renal function from baseline to 12 months; donor-specific anti-HLA antibodies presence and intensity (MFI); correlation of B7-1 positivity on immunofluorescence on biopsy with B7-1-expression in urine extracellular vesicles; adverse events; acute rejection episodes; blood pressure control; new onset diabetes; hyperlipidemia; graft survival; and patient survival. At 18 months, we will perform a chart review to check if patient remained or not on Belatacept, their renal function, proteinuria and biopsy-proven rejection events since trial termination.

Developing a **urinary biomarker to non-invasively detect patients with B7-1 expression on allografts** is another goal of this study. This will not only allow monitoring of treatment effectiveness and serving as secondary end-points but will also permit non-invasively screening for B7-1 positivity in patients in the future. Briefly, we will isolate RNA from urinary extracellular vesicles (EVs) of transplanted patients and detect B7-1 mRNA using "Droplet Digital" PCR system. EVs such as exosomes (40-100 nm in diameter) and microvesicles (100-1000 nm) are nanometer-sized vesicles released by cells including kidney podocytes to mediate cell-to-cell communication by delivering proteins and genetic materials such as mRNAs and microRNAs (13). We hypothesize that podocytes expressing B7-1 will shed EVs into the urine that will carry B7-1 mRNA. [name] laboratory at the Transplantation Research Center (Co-Investigator) optimized the isolation of high quality and quantity of RNA from urinary EVs of transplant patients (Figure 4).

Enrolled patients will have serum and urine collected at time of conversion and 12 months post-conversion. Urine will be processed for extracellular vesicles (EVs) and mRNA isolation. Samples will be stored at minus 80 degrees Celsius freezer until analysis. Future alternative approaches for characterization of B7-1 expression on kidney allografts involve determination of urinary B7-1 mRNA

[figure not shown]

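### The plan aims to detect B7-1-positive grafts from urine, but its only analysis of the marker, a Spearman correlation, gives neither sensitivity nor specificity

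*Combined protocol and SAP*

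**What the plan says.** Section 6 (Proposal) makes it a goal to develop a "urinary biomarker to non-invasively detect patients with B7-1 expression on allografts" and adds that this "will also permit non-invasively screening for B7-1 positivity in patients in the future". The secondary endpoint, listed in the Synopsis, Section 5 and Section 6, is worded as the "correlation of B7-1 positivity on immunofluorescence on biopsy with B7-1-expression in urine extracellular vesicles". Section 11 analyses it in one sentence: "Spearman correlations will be calculated between B7-1 positivity on immunofluorescence on biopsy with B7-1-expression in urine extracellular vesicles".

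No section plans a ROC curve, an AUC, a urinary cut-off, sensitivity or specificity, and no section projects how many of the 36 patients will be B7-1 positive.

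The data needed are already planned. Section 9.2.2 makes the urine assay a quantitative mRNA measurement. Entry requires an "Available biopsy specimen for B7-1 staining at recruitment time". The Schedule of Events puts research urine and biopsy staining in the same Screening column, with research urine again at the end of treatment. Section 6 also warns that "the B7-1 staining is undergoing further optimization".

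**The concern.** Detection and screening need two quantities: the share of positive grafts that the urine test finds, and the share of negative grafts that it wrongly flags. Spearman's rho between a yes/no biopsy result and a continuous urine value reports neither. It summarises the total number of wrongly ordered positive-negative pairs, and very different tests can share that total.

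Rho is also awkward as a measure of accuracy. With a yes/no biopsy result it cannot reach 1 on untied urine values, and its maximum depends on how many patients are positive. If few are positive, a rho near 0.5 may be close to the best attainable value and yet look moderate.

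The trial could therefore finish with the right samples and no planned statement of how well the urine test detects positive grafts. A cut-off chosen after the results are linked would tend to flatter the test, especially with few positives.

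**Working it through.** The plan states no rho, AUC, sensitivity, specificity or precision for this analysis, so there is no design figure to reproduce.

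**Inputs**
- n = 36 (Synopsis, Sections 6 and 11).
- Number positive, k: not stated, so assumed. Section 3 reports 15 of 123 indication biopsies positive: 15/123 = 12.2%, exact 95% CI 7.0% to 19.3%. Applied to 36 patients this gives 36 × 15/123 = 4.4, with a range of about 2.5 to 7. Section 3 also reports 4 of 8 positive in nephrotic syndrome (exact 95% CI 16% to 84%). Half of 36 is 18, used here as a high value.
- Biopsy result taken as yes/no, as worded; urine values untied unless stated.

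**Formula.** With k positives and no ties, rho = (2·AUC − 1) × sqrt(3k(n − k)/(n² − 1)), where AUC is the share of positive-negative pairs in the right order.

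**Step 1: same rho, different tests (k = 4).** There are 4 × 32 = 128 pairs. Suppose 13 are misordered. Then AUC = 115/128 = 0.898 and rho = (2 × 115/128 − 1) × sqrt(3·4·32/1295) = 0.797 × 0.5445 = 0.434. Rho depends only on the total of 13, not on which patients cause it.
- All 13 due to one positive that ranks below 13 negatives, the other three above every negative: specificity at full sensitivity is 1 − 13/32 = 19/32 = 59%. Sensitivity at full specificity is 3/4.
- The 13 spread as 4, 3, 3, 3: specificity at full sensitivity is 1 − 4/32 = 28/32 = 88%. Sensitivity at full specificity is 0/4.

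These are the minimum and maximum specificity at that rho.

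**Step 2: k = 7.** There are 7 × 29 = 203 pairs. With 20 misordered, AUC = 183/203 = 0.901 and rho = 0.803 × 0.686 = 0.551. One positive below 20 negatives gives 9/29 = 31%; spreading the 20 as six 3s and one 2 gives 26/29 = 90%.

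**Step 3: other counts, rho held near 0.43.** Specificity at full sensitivity can range over:

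| Positives | Lowest | Highest |
|---|---|---|
| 3 | 85% | 94% |
| 4 | 59% | 88% |
| 5 | 32% | 84% |
| 6 to 18 | 0% | 72% to 83% |

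**Step 4: ceiling of rho.** Setting AUC = 1 in the formula gives sqrt(3k(n − k)/(n² − 1)): 0.54 for k = 4, 0.69 for k = 7 and 0.87 for k = 18. Conversely, one AUC of 0.90 gives rho 0.44, 0.60 or 0.69 with 4, 9 or 18 positives.

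**Step 5: tied urine values.** Ties divide rho by sqrt(1 − Σ(t³ − t)/(n³ − n)), with t the size of each tied group. With k = 4 and 25 of 36 undetectable, 108 of 128 pairs in order (ties counted one half) gives AUC 0.844 and rho = 0.6875 × 0.5445/sqrt(1 − 15600/46620) = 0.459. At the detectable cut-off this fits 4/4 with 25/32, or 3/4 with 24/32. Ties also raise the ceiling: with k = 4 and 24 of 32 negatives undetectable, a perfect marker gives 0.65.

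**Step 6: precision of the added measures (exact 95% CI).** Sensitivity 4/4: 40% to 100%; 7/7: 59% to 100%. Specificity 19/32: 41% to 76%; 28/32: 71% to 96.5%.

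**The case against.** The strongest reply is that the analysis matches the endpoint, which is worded as a correlation in all three places. The detection language describes development and future use, and in a Phase I study sized on feasibility an association is a reasonable first step. That stands as far as it goes: Spearman should stay. It does not remove the gap, because Section 6 names detection as a goal of this study and no planned analysis addresses it.

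Three further points stand and limit the claim.
- A reader might infer that adding an AUC is the remedy. It is not: both markers in Step 1 have the same AUC, 0.898. Without ties and with k known, AUC is a rescaling of rho.
- A detectable-versus-undetectable cut-off would not separate that pair either. With untied values at most one can be undetectable; if it is the lowest, both markers show 4/4 and 1/32. Where many values are undetectable (Step 5), the two cases differ by one positive and one negative patient, which these data could not distinguish.
- The 59% rests on one badly ranked positive. It is an extreme, not a typical value.

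Small numbers are also a fair objection. They make the estimates descriptive, but an interval of 40% to 100% tells the reader more about detection than a single rho does.

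**Conclusion.** The concern holds: the planned analysis cannot answer the detection question, and the missing quantities are sensitivity and specificity. At k = 4 one rho leaves specificity at full sensitivity open between 59% and 88%; at k = 7, between 31% and 90%.

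A reader might take 4 of 36 as the trial's expected count. The documents do not say so. It is carried over from indication biopsies not selected for proteinuria, whereas enrolled patients have at least 1 g/day, so more may be positive. The gap is present at every count tried from 3 to 18.

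A reader might also infer that any rho near 0.5 is close to its maximum. That is so only with few positives; with 18 the ceiling is 0.87. The ceilings also assume a yes/no stain and untied urine. With a graded stain and all negatives at the lowest grade, the ceiling at k = 4 hardly moves (0.546 against 0.544).

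Priority is low: a cheap improvement to a secondary analysis, with no effect on the primary analysis.

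**What to change.** Keep the Spearman correlation and add a paragraph to Section 11. It should use the screening (pre-treatment) urine sample and the same positivity rule that defines the B7-1 groups in the primary analysis, with the stain version stated if the stain changes. It should plan:

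- (a) the ROC curve, with sensitivity and specificity across cut-offs, labelled exploratory;
- (b) sensitivity and specificity with exact 95% CIs at one cut-off fixed before urine and biopsy results are linked. Detectable versus undetectable is useful only if many values are undetectable; otherwise fix a numeric threshold;
- (c) AUC with a 95% CI, only as a summary that does not depend on the number positive. It does not replace (a) and (b);
- (d) the numbers positive and undetectable.

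The cost is one paragraph and a decision on the cut-off before linkage. Samples, assays, visits and endpoint wording are unchanged. The downside is wide intervals, so the results should be presented as descriptive.
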